1. VERSION HISTORY

This Statistical Analysis Plan (SAP) for study B8011011 is based on the protocol amendment 3 dated 28APR2021.

Table 1. Summary of Major Changes in SAP Amendments

Version	Version Date	Summary of Changes
1	28-Aug-2020	Not applicable (N/A)
2	24-Jun-2021	
The primary purpose of this amendment is to incorporate Sub-Study B into the statistical analysis plan. Additional updates were made for consistency or clarity. The term “patient” was replaced with the term “participant”.
 
Sec 2.1.1. “Sub-Study A” – removed PD-L1 secondary objectives and endpoint from Phase 1b of Sub-Study A; changed "PD-L1 expression" secondary endpoint to "OR by PD-L1 expression" added PRO objective and endpoint.
 
Sec 2.1.2. “Sub-Study B” – added Sub-Study B objectives, endpoints, and estimands.
 
Sec. 2.2 “Study Design” – removed 300 mg fixed dose for sasanlimab since the dose can be sub-study dependent. Figure 1 updated.
 
Sec. 2.2.2 “Sub-Study B Design” – added the whole new section to describe Sub-Study B design. .
 
Sec 3.1.1 “Phase 1b” – added DLT observation period for Sub-Study B.
 
Sec 3.1.2.2. “Sub-Study B” – added the primary endpoint of OR for Sub-Study B.
 
3.2.2.1. “Sub-Study A and Sub-Study B” – Definition of DR is clarified.
 
Sec. 3.2.3 “Pharmacokinetic endpoints” – added definitions for PK parameters.
 
Sec 3.2.4. “Immunogenicity endpoints” – added Sub-Study B treatments
 
Sec 3.2.6. “Patient Reported Outcomes endpoints” – added the whole section.
 
Sec 3.4.1. “Study drug, study treatment and baseline definitions” – added definitions related to Sub-Study B. Added definition of baseline for PRO and biomarker analyses.
 
Sec 4. “Analysis sets” – added footnote with Sub-Study B per-protocol analysis set criteria.
 
Sec 5.1.1.2. “Sub-study B” – added sample size determination for Sub-Study B.
 
Sec 5.1.2.2. “Sub-Study B” – added decision rules for Sub-Study B.
 
Sec 5.2. “General Methods” – added treatment groups definitions for Sub-Study B.
 
Sec 6.1.2.2.1. “Primary analysis” – added analysis of the primary endpoint of ORR for Sub-Study B.
 
Sec 6.2.2.3. “Duration of response” – corrected censoring condition by removing “date of randomization”.
 
Sec 6.2.3. “Pharmacokinetic endpoints” – added PK endpoints for Sub-Study B.
 
Sec 6.2.5. “Biomarker endpoints” – added analysis of PD-L1 biomarker for Sub-Study B.
 
Sec 6.2.6. “Endpoints for immunogenicity data” – added Sub-Study B, clarified definitions for ADA and NAb positive/negative in Table 14.
 
Sec 6.2.7.1. “Sub-Study A” – added analysis of PRO endpoints


		
Sec 6.5.3. “Study treatment compliance and exposure” – added related to Sub-Study B treatments, analyses of exposure, dose reductions, dose interruptions, dose delays.
 
Sec 6.6.1. “Adverse events” – added analyses related to Sub-Study B treatments.
 
Sec 7.2. “Sub-Study B” – added a statement that there will be no interim analysis in Sub-Study B.
 
Sec 8. “References” – added PRO and mTPI references, rearranged order alphabetically.
 
Appendix 2. Table “Next Dose Recommendation and the Interval probability of Target Toxicity and Overdosing at Next Dose” – added footnotes for notations.
 
Appendix 3. “List of Abbreviations” – new abbreviations added.

--	--	--

2. INTRODUCTION

This SAP provides the detailed methodology for summary and statistical analyses of the data collected in study B8011011. This document may modify the plans outlined in the protocol; however, any major modifications of the primary endpoint definition or its analysis will also be reflected in a protocol amendment.

Statistical analyses will be performed using cleaned electronic case report form (eCRF) data as well as non-CRF data (i.e., pharmacokinetics (PK), anti-drug antibody (ADA), neutralizing antibody (NAb), and biomarker data). The primary analysis for each sub-study will include all data up to a cut-off date corresponding to 12 months after the last participant receives the first dose of study treatment. The final analysis of the data will be performed after last participant last visit (LPLV).

Additional analyses of the data may be performed for publication or regulatory reporting purposes.

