3.1.2.1. Sub-Study A

- Durable OR is defined as a complete response (CR) or partial response (PR) according to RECIST v1.1 from the date of first dose of study treatment until the date of the first documentation of progressive disease (PD) and lasting for at least 10 months (298 days) from the date of first documentation of the CR or PR until progression or death. Both CR and PR must be confirmed by repeat assessments performed no less than 4 weeks after the criteria for response are first met.

Participants are considered to have had a durable OR if they had response lasting for ≥ 10 months (298 days). Each participant will have a durable objective response status (0: no durable OR; 1: durable OR).

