5.2.1. Data handling after the cut-off date

Data after the cut-off date may not undergo the cleaning process and will not be displayed in any listings or used for summary statistics, statistical analyses or imputations.

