5.2.8. Standard derivations and reporting conventions

The following conversion factors will be used to convert days into weeks, months or years: 1 week = 7 days, 1 month = 30.4375 days, 1 year = 365.25 days.

Demographics and physical measurements:

Age [years]: (year of given informed consent - year of birth)

The integer part of the calculated age will be used for reporting purposes.

For reporting conventions, mean and median should generally be displayed one more decimal place than the raw data and standard deviation should be displayed to two more decimal places than the raw data. Percentages will be reported to one decimal place. The rounding will be performed to closest integer / first decimal using the common mid-point between the two consecutive values. E.g., 5.1 to 5.4 will be rounded to an integer of 5, and 5.5 to 5.9 will be rounded to an integer of 6.

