6.1.2.1. Sub-Study A - Durable Objective Response

6.1.2.1.1. Primary analysis

Durable ORR is calculated as the proportion of participants in the full analysis population with durable OR along with a 2-sided 95% CI for durable ORR using the Clopper-Pearson method. Participants who do not have a post-baseline tumor assessment due to early progression of disease, who receive anti-cancer therapies other than the study treatments prior to reaching a CR or PR for 10 months, or who die, have PD, or stop tumor assessments for any reason prior to reaching a CR or PR for 10 months will be counted as non-responders in the assessment of Durable OR. Each participant will have a durable objective response status (0: no durable OR; 1: durable OR).

Refer to Section 6.2.2 for assessment of response.

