6.2.2.5. Progression-free survival

Progression-Free Survival (PFS) is defined as the time from the date of first dose of study treatment to the date of the first documentation of PD or death due to any cause, whichever occurs first.

PFS data will be censored on the date of the last adequate tumor assessment for participants who do not have an event (PD or death), for participants who start a new anti-cancer therapy

prior to an event (see Section 5.2.6) or for participants with an event after 2 or more missing tumor assessments. Participants who do not have an adequate baseline tumor assessment or who do not have an adequate post-baseline tumor assessment will be censored on the date of first dose of study treatment unless death occurred on or before the time of the second planned tumor assessment (i.e. ≤ 16 weeks after the first dose of study treatment) in which case the death will be considered an event.

The censoring and event date options to be considered for the PFS analysis are presented in Table 11.

$$\text{PFS (months)} = [\text{date of event or censoring} - \text{date of first dose of study treatment} + 1] / 30.4375$$

Table 11. Outcome and Event Dates for PFS Analyses

Scenario	Date of event/censoring	Outcome
No adequate baseline assessment	Date of first dose of study treatment ^a	Censored ^a
PD or death - After at most one missing or inadequate post-baseline tumor assessment, OR - ≤ 16 weeks after the date of first dose of study treatment	Date of PD or death	Event
PD or death - After 2 or more missing or inadequate post-baseline tumor assessments	Date of last adequate tumor assessment ^b documenting no PD before new anti-cancer therapy is given or missed tumor assessments	Censored
No PD and no death	Date of last adequate tumor assessment ^b documenting no PD before new anti-cancer therapy is given or missed tumor assessments	Censored
Treatment discontinuation due to 'Disease progression' without documented progression	Not applicable	Information is ignored. Outcome is derived based on documented progression only.
New anti-cancer therapy given	Date of last adequate tumor assessment ^b documenting no PD before new anti-cancer therapy is given or missed tumor assessments	Censored

^a However if the participant dies ≤ 16 weeks after the first dose of study treatment and did not initiate new anti-cancer therapy, the death is an event with date on death date.

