7. INTERIM ANALYSES

7.1. Sub-Study A

A futility analysis based on ORR will be performed in Phase 2 to allow early termination for futility after 30 participants are treated and followed for 2 on-treatment assessments (~4 months), without holding participant enrollment. If based on the observed ORR the probability of a true ORR \geq 48% is \leq 0.10, then the study will be stopped for futility. For example, the study will be stopped for futility if \leq 10 confirmed ORs are observed in the first 30 participants treated.

The probability of stopping the sub-study (if \leq 10 confirmed ORs are observed in the first 30 participants treated) under the alternative hypothesis is 0.014.

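### Sub-Study A: a primary cut-off 12 months after the last first dose is too short for a response that must last 298 days, so late-enrolled participants with ongoing responses lower the durable ORR and the power

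*SAP*

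**What the plan says.** - **Cut-off.** SAP Section 2 gives one rule for both sub-studies: the primary analysis takes data up to "a cut-off date corresponding to 12 months after the last participant receives the first dose of study treatment". A separate final analysis follows the last participant's last visit.
- **Later data.** Section 5.2.1: "Data after the cut-off date may not undergo the cleaning process and will not be displayed in any listings or used for summary statistics", nor for statistical analyses or imputations.
- **Endpoint.** Section 3.1.2.1 requires a confirmed CR or PR "lasting for at least 10 months (298 days) from the date of first documentation of the CR or PR". The clock starts at response, not at first dose.
- **Scoring.** Section 6.1.2.1.1 gives each member of the full analysis population a status of 0 or 1. Those who have other anti-cancer therapy, progression or death first, or who "stop tumor assessments for any reason prior to reaching a CR or PR for 10 months will be counted as non-responders", score 0. There is no censored or pending category.
- **Test.** Sections 5.1.1.1 and 5.1.2.1 test a durable ORR of at most 35% at one-sided 0.025. They claim at least 90% power at 55% with 62 participants and reject at 30 or more durable responders. The rule is applied when Phase 2 ends; no date or cut-off is attached to it.

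**The concern.** Each provision is reasonable alone, but together they do not fit. A minimum follow-up of 12 months from first dose must hold both the time to response and 298 days of response. For late-enrolled participants, anything but an early response runs past the cut-off. They are then scored the same as participants whose disease progressed, although their response is ongoing.

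This affects the only hypothesis test in Sub-Study A. Durable ORR would be underestimated and an active combination could miss 30 of 62 for administrative reasons. The power statement makes no allowance for this.

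**Working it through.** **1. The plan's own power figure.** The normal approximation (35% against 55%, one-sided 0.025, n = 62) gives power 0.901, so the stated 90% reproduces. The exact binomial with the plan's own rule gives P(X ≥ 30 | 62, 0.35) = 0.0205 and P(X ≥ 30 | 62, 0.55) = 0.880. The baseline below is 0.880, so there is no reserve to absorb a loss.

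**2. Time available to the last participant.** Section 5.2.8 sets "1 month = 30.4375 days", so 12 months = 365.25 days, and 365.25 − 298 = 67 days, or 9.6 weeks. (Ten months by that conversion is 304.4 days; the SAP fixes 298, which is used here.)

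**3. Cut-off needed, by week of first response.** The calendar count is 7 × week + 298 days. For the scan-documented count, an 8-weekly grid is inferred: Section 6.2.2.5 places the second planned assessment at 16 weeks or earlier, and Section 7.1 equates two assessments with about 4 months. The first scan at or after the calendar day is then taken.

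| First response | Calendar | Scan-documented |
|---|---|---|
| Week 8 | 56 + 298 = 354 d (11.6 mo) | week 56 = 392 d (12.9 mo) |
| Week 16 | 112 + 298 = 410 d (13.5 mo) | week 64 = 448 d (14.7 mo) |
| Week 24 | 168 + 298 = 466 d (15.3 mo) | week 72 = 504 d (16.6 mo) |

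By calendar, a week-8 response fits within 365 days with 11 days to spare. On the scan count it does not: the last scan before cut-off is day 336, only 280 days after the response. A week-16 response in the last participant fits neither.

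**4. Sensitivity without an accrual model.** If the last k participants cannot qualify, power is P(X ≥ 30 | 62 − k, 0.55): 0.851, 0.818, 0.780 and 0.690 for k = 1, 2, 3 and 5.

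**5. Sensitivity with an accrual model.** Assumptions, none of them in the SAP: true durable rate 55%; 62 enrolment dates evenly spaced over the accrual period; time to first response independent of enrolment date. Each participant's probability of being counted is 0.55 × the share of response times that fit before cut-off. Power is the exact probability that the sum reaches 30.

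| Split at weeks 8/16/24 | Accrual | Calendar: responders lost, power | Scan-documented: responders lost, power |
|---|---|---|---|
| 80/15/5 | 12 mo | 3.3%, 0.81 | 11.8%, 0.56 |
| 80/15/5 | 24 mo | 1.7%, 0.85 | 6.5%, 0.73 |
| 60/25/15 | 12 mo | 7.3%, 0.71 | 16.3%, 0.40 |
| 60/25/15 | 24 mo | 3.8%, 0.80 | 8.6%, 0.67 |
| All at week 8 | 12 mo | 0%, 0.88 | 8.1%, 0.69 |
| All at week 8 | 24 mo | 0%, 0.88 | 4.8%, 0.78 |

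Moving the evenly spaced dates by half an interval raises the 24-month scan-documented figures by 0.03 to 0.04 and leaves the rest unchanged. With 36-month accrual, power for the two mixed splits is 0.83–0.86 by calendar and 0.75–0.79 scan-documented. With 6-month accrual, the 80/15/5 split gives 0.73 and 0.21.

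**6. Direction.** Truncation can only remove durable responders from the count, so the probability of reaching 30 under the null stays at or below 0.0205.

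**The case against.** Several points limit the claim.

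- **Scoring of ongoing responders is implied, not written.** Section 6.1.2.1.1 does not list a participant who is still responding and still being scanned at cut-off. A reader might infer that the SAP declares such a participant a failure; it does not say so. This stands, but a mandatory 0/1 status with no later data leaves no other value for someone short of 298 days.
- **The scan rule is not in the endpoint definition.** A reader might infer that even a week-8 response always fails and that power falls to about one half. Both need the 298 days to be shown on a scan, on an 8-weekly grid carried past the two assessments that the SAP fixes. Section 6.2.2.3 does censor duration of response at the last adequate assessment, but that rule is written for another endpoint. The scan-documented figures are therefore conditional.
- **There is a no-loss case.** If every response appears by week 8 and calendar days count, power stays at 0.88. With slow accrual and calendar counting the loss is only about 2–5 points.
- **The test may be meant for later.** The decision rule refers to the end of Phase 2, and an analysis after the last visit is planned. A reader might infer that the test is firmly fixed at 12 months, or that the final analysis resolves the matter. The text settles neither: it calls the 12-month analysis primary, and nowhere makes the test wait for 298 days of follow-up.
- **The bias is conservative,** and a Kaplan-Meier 10-month response rate that censors ongoing responders is planned. But that rate is conditional on response and does not replace the 30-of-62 test.

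**Conclusion.** The conflict holds on the SAP's own figures: with a 12-month cut-off, the last-enrolled participants must first respond within about 67 days, and a week-16 response (410 days) cannot qualify under either counting rule. The consequences are an underestimated durable ORR and lower power, with no inflation of type I error.

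The size is not fixed by the document. Under the stated assumptions (true rate 55%, accrual over 12–24 months, the two mixed splits), power falls from 0.88 to about 0.71–0.85 by calendar count, or about 0.40–0.73 if scan-documented. The direction and mechanism are firm; the magnitude is illustrative and should be rerun with the sponsor's projected accrual and time to response.

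**What to change.** For Sub-Study A only, replace the 12-month rule. Set the primary cut-off at the date when every confirmed responder has had PD, death, new anti-cancer therapy or the end of tumor assessments, or has been followed for response for at least 298 days from first response. For first responses through week 24 this is about 15.3 months after the last first dose by calendar, or about 17 months if scan-documented.

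In the same change:

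- state that the 30-of-62 rule in Section 5.1.2.1 is applied at that cut-off;
- state whether the 298 days must be shown by an adequate tumor assessment;
- state how a responder still short of 298 days would be scored at any earlier data cut.

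Keep 12 months for Sub-Study B, whose primary endpoint has no duration requirement. The cost is a short text change in the SAP (and in the protocol if it repeats the rule) and a primary analysis about 3–5 months later. No extra participants are needed.

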2.1. Study Objectives, Endpoints, and Estimands

2.1.1. Sub-Study A

Table 2. Sub-Study A Objectives and Endpoints

Objectives	Endpoints
Primary:	Primary:
Phase 1b	Phase 1b

 To assess the dose limiting toxicity (DLT) rate and estimate the maximum tolerated dose (MTD) of sasanlimab in combination with encorafenib and binimetinib to recommend a phase 2 dose (RP2D) for the combination. 	
 DLTs during DLT-observation period.
Phase 2	Phase 2

 To assess the durable objective response rate (ORR) of sasanlimab in combination with encorafenib and binimetinib. 	
 Durable OR, defined as confirmed a complete response (CR) or partial response (PR) lasting for at least 10 months from the date of first CR or PR, as assessed by the investigator using RECIST v1.1.
Secondary:	Secondary:
Phase 1b	Phase 1b

 To assess the overall safety and tolerability of sasanlimab in combination with encorafenib and binimetinib. 	
 Adverse Events (AEs) graded according to the NCI-CTCAE v5.0 and changes in clinical laboratory parameters.

 To assess the anti-tumor activity of sasanlimab in combination with encorafenib and binimetinib. 	
 Durable OR and OR as assessed by the investigator using RECIST v1.1.

 To characterize the PK of sasanlimab, encorafenib, and binimetinib when administered in combination. 	
 PK parameters of sasanlimab (i.e., C_{trough}, C_{max}, T_{max}, AUC), encorafenib, binimetinib and applicable metabolites (i.e., C_{trough}) when administered in combination, as data permit.

 To evaluate the immunogenicity of sasanlimab when given in combination with encorafenib and binimetinib. 	
 ADA and nAb (i.e., incidence) against sasanlimab, as data permit.

Objectives	Endpoints
Secondary:	Secondary:
Phase 2	Phase 2

 To assess other measures of anti-tumor activity of sasanlimab in combination with encorafenib and binimetinib. 	
 Objective response (OR), duration of response (DR), time to response (TTR), progression free survival (PFS) by investigator assessment using RECIST v1.1, and overall survival (OS).

 To assess the overall safety and tolerability of sasanlimab in combination with encorafenib and binimetinib. 	
 AEs graded according to the NCI-CTCAE v5.0 and changes in clinical laboratory parameters.

 To characterize the PK of sasanlimab, encorafenib, and binimetinib when administered in combination 	
 PK parameters of sasanlimab, encorafenib, binimetinib, and applicable metabolites (i.e., C_{trough}) when administered in combination, as data permit.

 To evaluate the immunogenicity of sasanlimab when given in combination with encorafenib and binimetinib. 	
 ADA and nAb (i.e., incidence) against sasanlimab, as data permit.

 To assess the correlation between anti-tumor activity and PD-L1 expression in baseline tumor biopsies. 	
 OR by PD-L1 expression in baseline tumor samples.

 To assess the effects of sasanlimab, encorafenib, and binimetinib on patient-reported health-related quality of life. 	
 Health-related quality of life as measured by EORTC QLQ-C30/LC13
Tertiary/Exploratory:	Tertiary/Exploratory:
Phase 1b and Phase 2	Phase 1b and Phase 2

 To understand the relationship between the therapeutic intervention(s) being studied and the biology of the participant's disease. 	
 Measurements of biomarkers, consisting of DNA, RNA, protein, metabolites or defined cell types, resulting from analyses of peripheral blood and/or tumor tissue biospecimen obtained at baseline, on treatment or at end-of-study.
Phase 2	Phase 2

 To assess additional measure of anti-tumor activity of sasanlimab in combination with encorafenib and binimetinib. 	
 Depth of response by investigator assessment using RECIST v1.1.

Primary Estimand(s)

Phase 1b:

Primary Estimand (DLT): DLT rate estimated based on data from DLT-evaluable participants during the DLT-evaluation period (Cycle 1 – first 28 days of study treatment) in Phase 1b.

- Variable: Occurrence of DLTs.
- Analysis population: DLT-evaluable participants defined as participants who receive at least 1 dose of the combination study treatment in Phase 1b and either experience DLT during the DLT-evaluation period or complete the DLT-evaluation

period without DLT. Participants without DLTs who receive less than 75% of the planned dose of each study drug in Cycle 1 for reasons other than treatment-related toxicity are not evaluable for DLT. All participants deemed non-evaluable for DLT may be replaced.

- Population-level summary measure: DLT rate defined as the number of DLT-evaluable participants with DLTs in the DLT-evaluation period divided by the number of DLT-evaluable participants in the DLT-evaluation period.

Phase 2:

Primary Estimand (Durable OR): the treatment effect of sasanlimab + encorafenib + binimetinib assessed by the Durable ORR, based on Investigator assessment per RECIST v1.1, in the analysis population.

- Variable: Durable objective response defined as confirmed CR or PR according to RECIST v1.1 based on investigator assessment, lasting for at least 10 months from the date of first CR or PR until the date of the first documentation of PD, death, or start of new anticancer therapy. Both CR and PR must be confirmed by repeat assessments performed no less than 4 weeks after the criteria for response are first met.
- Analysis population: all participants who received at least 1 dose of study drug without regard to tolerability or duration of treatment.
- Population-level summary measure: Durable ORR defined as the proportion of participants in the analysis population with durable OR and 2-sided 95% CI for durable ORR using the Clopper-Pearson method. Participants who do not have a postbaseline tumor assessment due to early progression of disease, who receive anticancer therapies other than the study treatments prior to reaching a CR or PR for 10 months, or who die, have PD, or stop tumor assessments for any reason prior to reaching a CR or PR for 10 months will be counted as non-responders in the assessment of durable OR. Each participant will have a durable objective response status (0: no durable OR; 1: durable OR).

